		• To introduce the 2-week gradual uptitration regimen, to be used in case of re-initiation of study drug during TP3.
		• To amend the guidance for re-initiation of study treatment in the event of study treatment interruption in order to allow patients without the identified cardiovascular risk factors to re-initiate study drug at home.
		• To provide guidance regarding conduct of the study during the COVID-19 (coronavirus) pandemic.
		• To introduce guidance for subject monitoring and discontinuation in case of liver enzyme abnormalities.
		• To align the cardiovascular criteria for discontinuation with that used in Phase 3 clinical studies with ponesimod.

Ponesimod / ACT-128800/ JNJ-67896153 Multiple Sclerosis		EudraCT 2009-011470-15 EDMS-ERI-206617631
Protocol AC-058B202	Confidential	
Version 12		
15 March 2022, page 19/179		

Amendment	Date	Main reason(s)
9 19Oct20		• To inform study sites that the Independent Data Monitoring Committee (IDMC) will be disbanded after the clinical database closure of the last ponesimod double-blind study, in line with the disbandment date agreed per the IDMC Charter.
		• To provide further guidance on study conduct if/when ponesimod becomes commercially available during the study and patients are switched from study drug to commercially available ponesimod.
		• To align the safety reporting procedures with Janssen Safety processes and standards following the integration of Actelion Safety into Janssen Safety.
		• To clarify procedures related to the reporting of multiple sclerosis (MS) relapses and align with the wording in the protocol for the ongoing Phase 3 study (AC-058B303/OPTIMUM-LT).
10	04May21	• To align instructions related to vaccination to those in the Investigator's Brochure.
		• To introduce the transition of paper Case Report Form (CRF) to electronic Case Report Form (eCRF).
		 To further clarify guidance regarding conduct of the study during the COVID-19 (coronavirus) pandemic and the deployment of COVID-19 vaccines. To update sponsor contact information.

EudraCT 2009-011470-15 EDMS-ERI-206617631

Ponesimod / ACT-128800/ JNJ-67896153 Multiple Sclerosis Protocol AC-058B202 Version 12 15 March 2022, page 20/179

Confidential

TITLE	Multicenter, randomized, double-blind, parallel-group extension to study AC-058B201 to investigate the long-term safety, tolerability, and efficacy of 10, 20, and 40 mg/day					

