- When feasible, patients will be switched from TP2 to TP3 at the earliest scheduled visit, following approval of protocol version 8 by ECs/IRBs and health authorities, and after having signed the revised Informed Consent Form. The day of the first open-label dose of ponesimod 20 mg will correspond to the start of TP3. Patients not enrolling into TP3 will have to perform the EOT3 visit.
- All patients receiving 10 mg ponesimod during TP2 will receive a maintenance dose of 20 mg ponesimod during TP3, if they agree to continue in TP3. Patients receiving 20 mg ponesimod will continue with 20 mg ponesimod. Treatment allocation during TP1 and TP2 will not be revealed. All patients must be monitored at the investigational site for at least 6 hours after the first dose administration in TP3 [see Section 3.12.2].
- All visits will be performed every 12 weeks.

End-of-treatment

- The EOT visit (EOT2 or EOT3) in the extension study, at an individual patient's level, should not be later than one day after the last dose of ponesimod.
- Patients who prematurely discontinue study drug during the TP1, TP2, or TP3 of the extension study must have their EOT2 or EOT3 visit as soon as possible but no later than 5 days after the last dose of study drug.
- EOT2 visit must be performed by patients discontinuing study drug during / at the endof-treatment period 1.
- EOT3 visit must be performed by patients discontinuing study drug during / at the endof-treatment period 2 or TP3.
- The EOT3 visit must also be performed by patients completing study treatment due to availability of commercially available ponesimod. Commercially available ponesimod may be initiated on the day after last intake of study drug.

Safety Follow-up period

For TP1:

In the case of discontinuation from study drug before Visit P1, safety will be followed up for 30 days after last dose of study drug. There are two Safety Follow-up visits:

- Visit E14 (Follow-up Visit E1): 8 days after the last study drug intake.
- Visit E15 (Follow-up visit E2): 30 days after the last study drug intake.

Ponesimod / ACT-128800 / JNJ-67896153 Multiple Sclerosis Protocol AC-058B202 Version 12 15 March 2022, page 56/179

Confidential

EudraCT 2009-011470-15 EDMS-ERI-206617631

For TP2 and TP3:

In the case of discontinuation from study drug after Visit P1, safety will be followed up for 90 days after last dose of study drug. There are three Safety Follow-up visits:

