3.12.4 Safety Follow-up period

All patients, whether they performed the EOT2 or EOT3 visit or prematurely discontinued from study drug, will have to perform the corresponding Safety Follow-up visits:

TP1:

In the case of discontinuation from study drug before Visit P1, safety will be followed up for 30 days after last dose of study drug. There are two Safety Follow-up visits:

- Follow-up Visit E1 (Visit E14):
 - 8 days after the last study drug administration (EOT2 + 7 days)
- Follow-up visit E2 (Visit E15):
 - 30 days after the last study drug administration

TP2 and TP3:

In the case of discontinuation from study drug after Visit P1 safety will be followed up for 90 days after last dose of study drug. There are three Safety Follow-up visits:

- Follow-up visit 1 (FU1):
 - 8 days after the last study drug administration
- Follow-up visit 2 (FU2):
 30 days after the last study drug administration
- Follow-up visit 3 (FU3):
 90 days after the last study drug administration

These visits and assessments will also be conducted for patients who have switched to commercially available ponesimod. Note that for these patients, the timing of each Safety Follow-up visit refers to the time since the last **study drug** administration, independent of any administration of commercially available ponesimod.

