5. STATISTICAL ANALYSES

5.1. General Considerations

5.1.1. Dates, times and days

Core study treatment start date: date of first administration of study drug (ponesimod or placebo) in AC-058B201.

Extension study treatment start date: date of first administration of ponesimod in AC-058B202.

Ponesimod start date (PSD): date of first administration of ponesimod:

- for subjects randomized to ponesimod in the core study, this is the date of the first study drug administration in the core study.
- for subjects randomized to placebo in the core study and enter the extension, this is the date of the first study drug administration in the extension study.

Ponesimod EOT / ponesimod end date: defined as the latest study treatment end date as recorded on the Study Drug Log (ECENDTC in SDTM.EC where ECCAT = 'STUDY DRUG LOG').

Extension End-of-Treatment (eEOT) / **extension study treatment end date:** equal to the Ponesimod EOT / Ponesimod end date as defined above for subjects entering the extension study. Missing for subjects not entering the extension study.

Core End-of-Study (cEOS) date: the EOS date in the core study, defined as DSSTDTC in SDTM201.DS, where DSSCAT='STUDY TERMINATION'. If the subject died, then EOS date is set to death date, where death date is defined as SDTM201.DD.DDDTC.

Extension End-of-Study (eEOS) date: the EOS date in the extension study, defined as DSSTDTC in SDTM202.DS, where DSSCAT='STUDY TERMINATION'. If the subject died, then EOS date is set to death date, where death date is defined as SDTM202.DD.DDDTC. Missing for subjects not entering the extension study.

Last study date: defined as core EOS date for subjects who did not enter the extension study, and Extension EOS date for subjects who did enter the extension study.

Ponesimod Study Day: defined as the number of days elapsed since ponesimod start date (PSD) plus 1 (e.g., Ponesimod Study Day 1 is the day of first administration of ponesimod). For dates prior to ponesimod start date (PSD), study day is the negative number of days elapsed between the date under consideration and the day of first administration of ponesimod. Therefore, the ponesimod study day is always different from 0.

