5.4.1. Exposure and Compliance

5.4.1.1. Exposure to study treatment

All ponesimod drug administration data is taken from the study drug log and stored in SDTM.EC. ECSTDTC where EC.ECCAT = 'STUDY DRUG INTAKE'. The two EC datasets are concatenated for the purposes of this analysis.

Ponesimod exposure (years) for any given exposure period is derived as:

-[(Treatment end date - ponesimod start date + 1 day) - (End date of pregnancy interruption - Start date of pregnancy interruption + 1 day)] / 365.25, for subjects with planned pregnancy interruption and restart of the treatment,

- (Treatment end date - ponesimod start date + 1 day) / 365.25, regardless of interruptions, for all other subjects.

Duration of planned pregnancy study drug interruption (days) is defined as: min (EOS date, end date of pregnancy interruption) – Start date of pregnancy interruption + 1 day
In case of multiple planned pregnancies, all intervals between start date and end date of each pregnancy interruption will be subtracted from exposure.

Duration of planned pregnancy is excluded from all definitions of exposure duration and compliance with study treatment.

The following variables are derived for ponesimod exposure:

	1	
Exposure period	Start date	End date
Ponesimod exposure	First administration of	Last administration of ponesimod in the
during the core study	ponesimod in the core study	core study
(years)		
Ponesimod exposure	First administration of	Last administration of ponesimod in TP1
during TP1 (years)	ponesimod TP1	_
Ponesimod exposure	First administration of	Last administration of ponesimod in TP2
during TP2 (years)	ponesimod TP2	_
Ponesimod exposure	First administration of	Last administration of ponesimod in TP3
during TP3 (years)	ponesimod TP3	
Ponesimod exposure	First administration of	Max of [last administration of ponesimod
during AP3 (years)	ponesimod (in core or TP1)	in the core study, last administration of
		ponesimod in TP1, last administration of
		ponesimod in TP2, last administration of
		ponesimod in TP31

Table 10: Ponesimod exposure variables

AP = Analysis Period; TP = Treatment Period.

If end date is missing on last record in EC (e.g., if a subject is lost to follow-up), then date of last administration is taken as DS.DSSDTC when DSSCAT = 'Study termination'.

For each of the variables defined in Table 10 above, the following corresponding exposure variables are derived:

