- Incidence of treatment-emergent PFT outliers [as defined above frequency counts, percentages, where percentages are based on the number of subjects at risk, i.e. number of subjects with at least 1 post-baseline value in that category during the analysis period (AP3 on the PAS) by treatment group.

The following plot is produced:

A plot of %pred FEV₁ values over time (including FU visits), by analysis visit (AP3 on the PAS) by treatment group;

By Post-Treatment DMT Subgroup

The following summaries are produced for PFT parameters by Post-Treatment DMT subgroup, as defined in Section 5.5.6 (pooling across all treatment groups):

- Summary of absolute values at ponesimod baseline, at last on-treatment and at each followup visit (FU7, FU30, FU90 and Last FU) for PFT parameters: descriptive statistics by analysis visit (AP3 on the PAS), by Post-Treatment DMT subgroups ((Any DMT, including ponesimod), No DMT).
- Summary of absolute change from ponesimod baseline to last on-treatment and each follow-up visit (FU7, FU30, FU90 and Last FU) for PFT parameters: descriptive statistics by analysis visit (AP3 on the PAS), by Post-Treatment DMT subgroup ((Any DMT, including ponesimod), No DMT).
- Summary of percent change from ponesimod baseline to last on-treatment and each followup visit (FU7, FU30, FU90 and Last FU) for PFT parameters: descriptive statistics by analysis visit (AP3 on the PAS), by Post-Treatment DMT subgroup ((Any DMT, including ponesimod), No DMT).

The following plots are produced:

- A plot of ponesimod baseline, last-on-treatment and follow-up values for %pred FEV₁, by analysis visit (AP3 on the PAS), by Post-Treatment DMT subgroup ((Any DMT, including ponesimod), No DMT).
- A plot of absolute change from ponesimod baseline to last-on-treatment and follow-up values for %pred FEV₁, by analysis visit (AP3 on the PAS), by Post-Treatment DMT subgroup ((Any DMT, including ponesimod), No DMT).

By Total Exposure Duration Subgroup:

The following summaries are produced for PFT parameters by the Total Exposure Duration subgroup, as defined in Section 5.5.6 (pooling all treatment groups).

- Summary of absolute values at ponesimod baseline, at last on-treatment and at each followup visit (FU7, FU30, FU90 and Last FU) for PFT parameters: descriptive statistics by analysis visit (AP3 on the PAS), by the Total Exposure Duration subgroup.

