5.5.6. Definition of Subgroups

The following subgroups are defined for the Follow-up Phase:

- (i) Post-treatment DMT: A patient in the Follow-up Phase is assigned to the "Any DMT, including ponesimod" category if there is a record in CMDECOD in SDTM.CM for any of the therapies listed in Table 11 in Section 6.5.1 and the corresponding CMENDTC in SDTM.CM is on or after the ponesimod EOT date or ongoing at EOS date. In cases where CMENDTC is missing and CM is not ongoing, it should be checked whether CMSTDTC is on or after the ponesimod EOT date. Otherwise, the patient is assigned to the "No DMT" category.
- (ii) Total Exposure Duration: A patient in the Follow-up Phase is assigned to one of the following categories "Less than or equal to 4 years", "Greater than 4 and Less than or equal to 8 years", "Greater than 8 years", based on their Ponesimod exposure duration during AP3 (years), as defined in Table 10 in Section 5.4.1.1. This subgroup will be considered only for PFT.

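### Follow-up lung-function tables by exposure duration do not separate patients off ponesimod from those on commercial ponesimod, and nearly all of the latter fall in the over-8-years category

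*SAP*

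**What the plan says.** SAP 5.5.6 puts each Follow-up Phase patient into one of three categories (up to 4 years, over 4 to 8 years, over 8 years), "based on their Ponesimod exposure duration during AP3 (years), as defined in Table 10 in Section 5.4.1.1". It adds: "This subgroup will be considered only for PFT". SAP 5.4.5.5 then gives the output: "The following summaries are produced for PFT parameters by the Total Exposure Duration subgroup, as defined in Section 5.5.6 (pooling all treatment groups"). The tables cover ponesimod baseline, last on-treatment, FU7, FU30, FU90 and Last FU, with two plots of percent-predicted FEV1.

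Exposure counts study drug only. SAP 5.1.1 takes the ponesimod end date from study records: it is "defined as the latest study treatment end date as recorded on the Study Drug Log". SAP 5.4.1.1 computes exposure as "Treatment end date - ponesimod start date + 1 day) / 365.25, regardless of interruptions, for all other subjects". Only planned-pregnancy interruptions are deducted.

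On commercial supply, protocol 3.1.1 states: "Commercially available ponesimod may be initiated on the day after last intake of study drug". Protocol 3.12.4 states of the safety follow-up: "These visits and assessments will also be conducted for patients who have switched to commercially available ponesimod". It times each visit from the last study dose whatever commercial drug has been taken. Protocol 3.11.2.4 schedules lung-function tests at FU1, FU2 and FU3.

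A separate set of tables in SAP 5.4.5.5 splits follow-up lung function by post-treatment therapy: any disease-modifying therapy (ponesimod included) against none. The two splits are not crossed.

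**The concern.** A table of follow-up values by length of exposure invites a question about reversibility: does lung function recover as well after long treatment as after short treatment? Protocol 1.3.2.4 reports that lung-function changes reversed once ponesimod was stopped.

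For a patient who started commercial ponesimod the next day, the values labelled as follow-up are on-drug values. If such patients were spread evenly over the exposure categories, they would blur every column alike. They are not spread evenly. Commercial supply came late in the study, so they collect in the longest category, and continued dosing moves with the variable that the table compares. A deficit that persists in the over-8-years column could mean loss of reversibility or simply that patients kept taking the drug, and the planned output cannot tell the two apart.

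**Working it through.** The plan states no figure to reproduce for this descriptive table. The check has three parts.

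**1. Which category do switchers fall in?**

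Inputs:
- Latest possible ponesimod start: the protocol synopsis puts the last patient's first extension visit in Q2 2011, so 30 June 2011 at the latest (a former placebo patient).
- Earliest possible switch: the documents give no launch date. The protocol's amendment history, used here only to date events, gives this reason for Amendment 9 of 19 October 2020: "To provide further guidance on study conduct if/when ponesimod becomes commercially available during the study". Supply was then still in the future.
- Largest deduction: 81 weeks for planned pregnancy (protocol 3.6.2), that is 81 × 7 / 365.25 = 1.55 years. Appendix 1 section D applies that limit to the total.

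Formula: minimum exposure = (switch date − start date + 1) / 365.25.

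| Switch date | Latest starter | Less a full 81 weeks |
|---|---|---|
| 19 Oct 2020 (Amendment 9) | 3,400 / 365.25 = 9.31 years | 7.76 years |
| 15 Mar 2022 (protocol version 12) | 10.71 years | 9.16 years |

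Patients on ponesimod since the core study started at least 24 weeks earlier (by 13 January 2011), which gives at least 9.77 years at 19 October 2020. Even the latest starter reached 8 years on 30 June 2019. A switcher can fall at or below 8 years only by combining a near-maximal pregnancy interruption, a start after about 1 April 2011 and a switch before about 17 January 2021.

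Rough consistency check: for patients still on drug at the interim cut-off of 31 March 2019, the same start dates give 7.75 to 9.46 years. The protocol's median of 8.02 years in the 20 mg group (1.3.2.4) lies inside that range.

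**2. Are the follow-up values on drug or off drug?**

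Protocol 1.3.2.1 gives a terminal half-life of about 32 hours. Residual fraction = 2^(−hours/32). At day 8 after a true stop this is 2^(−192/32) = 2^(−6) = 1.6%, and at day 30 it is practically nil. Follow-up values are therefore off drug for patients who stop and on drug, at every visit, for next-day switchers.

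**3. What does mixing do?**

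Let R be the true mean recovery off drug (last on-treatment to follow-up). Let s be the share of over-8-years follow-up values taken on commercial ponesimod. Assume the same on-drug effect in both kinds of patient and no recovery while dosing continues. Then

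recovery shown = (1 − s) × R + s × 0 = (1 − s) × R.

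| Assumed s | Share of true recovery shown |
|---|---|
| 25% | 75% |
| 50% | 50% |
| 75% | 25% |

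In the two shorter categories s is close to zero. If R is zero, nothing is masked whatever s is.

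**The case against.** A reader might infer that lung effects after long exposure will look less reversible than they are, or that switchers dominate the over-8-years group. The documents do not support either statement:
- The number of switchers is not given. Availability depends on country, and patients may also run to 636 weeks or stop for other reasons (protocol 1.4.6).
- A next-day start is permitted, not required.
- Protocol 1.3.2.4 describes the clinically relevant FEV1 decrease 2 to 6 hours after 40 mg or more. Patients with long exposure had left 40 mg at Visit P1, and on-treatment tests are pre-dose. No trough effect at 20 mg is stated.

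Switchers have also tolerated the drug for years and may have a smaller effect. The direction is therefore firmer for within-patient recovery than for the absolute level.

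The SAP's split by post-treatment therapy already gives an off-drug display. It answers part of the point, but it pools all exposure durations and merges ponesimod with every other therapy. No planned output shows off-drug lung function by exposure duration.

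Neither document says that these tables are meant to test reversibility; SAP 6.2.3 says only that they were thought important. All analyses are exploratory and descriptive, so interpretation is at stake, not error rates.

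Finally, the exposure categories differ in other ways. Decline in lung function can itself end treatment. Patients who stop in TP1 have no 90-day visit. Values in litres carry ageing: by the SAP's equations predicted FEV1 falls 9 × 0.025 = 0.23 L (women) to 9 × 0.029 = 0.26 L (men) over nine years. All of this stands, and separating switchers does not remove it.

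**Conclusion.** The point holds as a confounding problem of unknown size. Three things follow from the documents: the exposure tables and plots place on-drug and off-drug follow-up values together, switchers fall almost entirely in the over-8-years category, and the shorter categories are essentially free of commercial ponesimod (though not necessarily of other therapies). If a material share switch and there is a lung-function effect at 20 mg, recovery in that category could look smaller than it is, by the factor 1 − s. The conclusion rests on no switch before 19 October 2020 and on the assumptions stated for the mixing formula. It does not establish that the final table will mislead, only that a reader could not separate persistence from continued dosing.

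**What to change.** In the exposure-duration tables of SAP 5.4.5.5 and both percent-predicted FEV1 plots:
- Exclude from FU7, FU30, FU90 and Last FU any lung-function value taken on or after the recorded start date of commercial ponesimod (SDTM.CM). Apply this before the window value, or the last value, is selected.
- Show the excluded values in a separate column for patients continuing on commercial ponesimod.
- Keep baseline and last on-treatment values for everyone.
- Footnote any other post-treatment disease-modifying therapy.

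A visit-level rule is better than restricting to the SAP 5.5.6 category without post-treatment therapy. That flag is per patient, so it would discard valid values taken before a delayed commercial start, or from patients who later began an unrelated therapy.

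The cost is SAP wording and one date filter. The start date is already collected (protocol 3.11.5.3), and ponesimod is already listed in SAP Table 11. The off-drug over-8-years group will be smaller, and its size should be shown at each visit. Selection, ageing on the litre scale and the missing 90-day visit after TP1 remain and should be noted beside the tables.

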5.5. Other Analyses

5.5.1. Pharmacokinetics

Blood samples were collected in order to provide information about study drug exposure in the target population, at various time points during the study as specified in the protocol schedule, and summarized below, for pharmacokinetic (PK) and pharmacokinetic /pharmacodynamic (PK/PD) evaluations.

Plasma concentrations of ponesimod are determined at trough (pre-dose):

- **TP1**: on Days 8 and 15 (Visits E2 and E3) and at Visits E4 (Week 4), E7 (Week 24), E9 (Week 48), and E13 (EOT2)
- **TP2 and TP3**: P2 (Week 12), P7 (Week 72), P14 (Week 156) and P22 (Week 252), as applicable

Although plasma concentration results were intended to be collected at the visits mentioned above, the study design evolved to allow participants to transition from TP1 anytime after Week 48 up to 90 days after EOT2, and be enrolled into TP2 starting with Visit P1. Thus, not all participants had blood samples collected at all visits.

In addition, some participants also had plasma concentration samples collected at visits not assigned in the protocol.

To address the variability of transition from TP1 to TP2, the following rules will be instituted to map the plasma collection dates for a participant to the planned plasma collection timepoints in the protocol.

Based on the protocol the following windows are allowed at the different timepoints: Days 8, 15: +-1 day, Week 4: +- 2days, further Weeks: +- 14 days:

- If TP1start date ≤ Plasma collection date < start of TP2 start date or TP1 start date ≤ plasma collection date (for subjects who did not enter TP2): Let the time difference be denoted Diff = Plasma collection date – TP1 start date +1 Day 8 (Visit E2): (7 ≤ Diff ≤ 9); Day 15 (Visit E3): (14 ≤ Diff ≤ 16); Week 4 (Visit E4): (26 ≤ Diff ≤ 30); Week 24 (Visit E7): (154 ≤ Diff ≤ 182); Week 48 (Visit E9): (322 ≤Diff ≤ 350); Week 96 (Visit E13 EOT2): 658 ≤ Diff ≤ 686)
- If TP2 start date <= Plasma collection date: Let the time difference, denoted Diff = Plasma collection date – TP2 start date +1 Week 12 (Visit P2): (70 ≤ Diff ≤ 98); Week 72 (Visit P7): (490 ≤ Diff ≤ 518); Week 156 (Visit P14): (1078 ≤ Diff ≤ 1106); Week 252 (Visit P22): (1750 ≤ Diff ≤ 1778);

Descriptive statistics by treatment period and by dose for the following pre-dose samples will be presented:

- TP1: Days 8 and 15, and Weeks 4, 24, 48, and 96
- TP2 and TP3: Weeks12, 72, 156, and 252

The following summaries are produced for trough level plasma concentrations at each time point of measurement by treatment group:

• Summary of absolute values of PK parameters: descriptive statistics by analysis visit

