1.3.2.1 Clinical pharmacology

The PK profile of ponesimod is characterized by low variability. The terminal elimination half-life is about 32 h. There is approximately two-fold accumulation with repeated o.d. oral dosing, and steady-state is achieved within 4 5 days. There is a good correlation between the plasma concentration of ponesimod and the reduction of total lymphocyte count in peripheral blood. Food, age, race or sex do not appear to relevantly affect the PK or PD of ponesimod. The drug-drug interaction potential of ponesimod is judged to be low based on current nonclinical and clinical data.

More detailed information can be found in the Investigator's Brochure [Ponesimod IB].

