- On Visit E2 (Day 8 of the extension study; day of first (mock) uptitration), the study drug will be administered in the clinical setting and either uptitrated to the dose of 20 mg ponesimod, or a mock dose titration will take place. The patient must be monitored at the investigational site for at least 6 hours after dose administration on Day 8 [see Section 3.12.2].
- On Visit E3 (Day 15 of the extension study; day of second (mock) uptitration), the study drug will be administered in the clinical setting and either up-titrated to the dose of 40 mg ponesimod, or a mock dose titration will take place. The patient must be monitored at the investigational site for at least 6 hours after dose administration on Day 15 [see Section 3.12.2].
- On Day 22 of the extension study the site will call the patient to obtain information on health status / AEs.
- From Visit E4 (Week 4, Day 29 of the extension study) visits will be performed every four weeks until Visit E6 (Week 12).
- From Visit E6 (Week 12) until the end of the treatment period of up to 96 weeks (Visits E6 to E13; Weeks 12, 24, 36, 48, 60, 72, 84 and 96) or until study drug discontinuation, visits will be performed every 12 weeks.

TP2 and TP3 (up to 540 weeks):

- Patients will be switched from TP1 to TP2 at Visit P1. As soon as a patient has completed at least Visit E9 (Week 48) of TP1 (being still on treatment) following approval of global protocol version 3, Visit P1 can be scheduled as the next regular visit (12 weeks after Visit E9 or E10 or E11 or E12). After completing Visit E13 (EOT2), Visit P1 must be scheduled as soon as possible, provided study drug was not discontinued for longer than 3 months and a re-initiation / uptitration must be performed, if applicable.
- All patients will be switched from capsules to tablets at Visit P1.

Ponesimod / ACT-128800 / JNJ-67896153 Multiple Sclerosis Protocol AC-058B202 Confidential		EudraCT 2009-011470-15 EDMS-ERI-206617631
Version 12		
15 March 2022, page 55/179		

- All patients receiving 40 mg ponesimod during TP1 will be re-randomized to 10 or 20 mg ponesimod in a 1:1 ratio. Patients receiving 10 mg and 20 mg ponesimod will continue with these respective maintenance doses.

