3.12.2.8 Visit E13 (Week 96) – EOT2

The visit window for this visit is ± 14 days.

A Visit E13 (EOT2 visit) will be performed:

- For patients completing Week 96 according to the protocol and who did not sign yet the informed consent for the protocol version 3 in order to enter into TP2:
 - One day after the last dose of study drug
- For patients who discontinue study drug prematurely:
 - As soon as possible but no later than 5 days after the last dose of study drug

At Visit E13 (EOT2) the following assessments must be performed:

- Change in concomitant medication, if any;
- Physical examination (including careful skin examination);
- PFTs (FEV₁, FVC);
- Ophthalmological examination (best corrected visual acuity, low contrast visual acuity, visual fields, and dilated ophthalmoscopy);
- 12-lead ECG and SBP/DBP (under the responsibility of the physician evaluating cardiac safety assessments);
- Standard 2D/Doppler echocardiography (at selected centers);
- Laboratory tests (central laboratory) in fasting condition:
 - Hematology, blood chemistry, urinalysis;
 - Pregnancy test;
- A blood sample for PK assessments will be taken;
- EDSS and FS scores (assessed by the independent evaluating neurologist);

Ponesimod / ACT-128800 / JNJ-67896153 Multiple Sclerosis Protocol AC-058B202 Version 12 15 March 2022, page 99/179

Confidential

EudraCT 2009-011470-15 EDMS-ERI-206617631

- MRI examination;
- Chest X-ray;
- Recording of AEs and SAEs.

When the patient has completed all scheduled assessments, Visit E14 (Follow-up Visit E1) will be scheduled 8 days after the last dose of study drug.

3.12.3 Extension treatment periods 2 and 3

Patients who completed at least Visit E9 from TP1 are allowed to enroll into TP2 starting with Visit P1. Patients who have already completed treatment up to Visit E13 (EOT2) may still be enrolled into TP2, provided study drug was not discontinued for longer than 3 months. In this case, Visit P1 must be scheduled as soon as possible and, if applicable, patients must undergo a study drug re-initiation and/or uptitration.

The TP2 and TP3 consist of the visits and assessments described in Sections 3.12.3.2 and 3.12.3.3.

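### SAP 5.5.1 centres its eight week-based PK windows one day early, and its sample mapping has no on-drug condition

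*SAP*

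**What the plan says.** SAP 5.5.1 maps each plasma sample to a planned timepoint through a day count. In TP1 this is "Diff = Plasma collection date – TP1 start date +1", and from the start of TP2 it is "Plasma collection date – TP2 start date +1", so the first day of the period is Day 1. The section attributes its tolerances to the protocol: "Days 8, 15: +-1 day, Week 4: +- 2days, further Weeks: +- 14 days". It then writes out ten windows, among them "Week 4 (Visit E4): (26 ≤ Diff ≤ 30); Week 24 (Visit E7): (154 ≤ Diff ≤ 182". The mapped values are summarised as trough concentrations by timepoint and treatment group.

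Protocol 3.1.1 fixes the study day of Week 4: "From Visit E4 (Week 4, Day 29 of the extension study) visits will be performed every four weeks". Protocol 3.12.2.5 gives that visit a window of ± 2 days. SAP Table 3 sets the general visit targets at Day 29 for Week 4, 85 for Week 12, 169 for Week 24, 337 for Week 48, 505 for Week 72 and 673 for Week 96.

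The mapping conditions in SAP 5.5.1 refer only to the collection date and the TP1 and TP2 start dates. SAP 1.2.3 counts interruptions as part of the treatment period, and Protocol 3.6.2 allows interruptions of up to 12 weeks (81 for a planned pregnancy). Protocol 3.12.2.8 takes a PK sample at EOT2. For patients who stop early, that visit is due "As soon as possible but no later than 5 days after the last dose of study drug". On elimination, Protocol 1.3.2.1 states: "The terminal elimination half-life is about 32 h".

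**The concern.** There are two separate defects in one rule.

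The first is a day-count error. If Day 1 is the period start, Week w falls on Day 7w + 1. The Day 8 and Day 15 windows follow that convention and the week-based windows do not. A sample taken on the last day the protocol allows is then left out of the by-timepoint summary, while one taken a day before the window opens is let in.

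The second is the missing on-drug condition, and it matters more. A trough concentration describes a patient who took the previous day's dose. A rule based on calendar dates cannot tell such a patient from one who stopped several days earlier or is in an interruption. Any such sample that lands in a window pulls the summarised trough down. PK/PD relationship analyses are not planned for the Final CSR (SAP 5.5.3), so this table is the report's main statement of exposure.

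**Working it through.** **Day count.** Inputs are the Diff definitions, tolerances and windows in SAP 5.5.1. With Day 1 as the start date, the window for Week w with tolerance t is (7w + 1 − t) to (7w + 1 + t).

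| Timepoint | t | SAP window | SAP centre | 7w + 1 | Window on 7w + 1 |
|---|---|---|---|---|---|
| Day 8 | 1 | 7–9 | 8 | named day 8 | 7–9 |
| Day 15 | 1 | 14–16 | 15 | named day 15 | 14–16 |
| Week 4 | 2 | 26–30 | 28 | 29 | 27–31 |
| Week 24 | 14 | 154–182 | 168 | 169 | 155–183 |
| Week 48 | 14 | 322–350 | 336 | 337 | 323–351 |
| Week 96 | 14 | 658–686 | 672 | 673 | 659–687 |
| TP2/TP3 Week 12 | 14 | 70–98 | 84 | 85 | 71–99 |
| TP2/TP3 Week 72 | 14 | 490–518 | 504 | 505 | 491–519 |
| TP2/TP3 Week 156 | 14 | 1078–1106 | 1092 | 1093 | 1079–1107 |
| TP2/TP3 Week 252 | 14 | 1750–1778 | 1764 | 1765 | 1751–1779 |

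A centre of 7w reproduces all eight week-based SAP windows exactly. It fits only a Diff without the + 1, and the Day 8 and Day 15 windows would then be wrong. Every shift is exactly −1 day. The share of allowed days lost is 1/5 = 20% at Week 4 and 1/29 = 3.4% at each other week.

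**Residual level off drug.** With mono-exponential decay and a 32 h half-life, the level d days after the last dose, relative to the 24 h trough, is 2^(−(24d − 24)/32):

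- d = 2: 2^(−0.75) = 0.59
- d = 3: 2^(−1.5) = 0.35
- d = 4: 2^(−2.25) = 0.21
- d = 5: 2^(−3) = 0.125
- d = 84 (12 weeks): effectively zero

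If a share p of the samples in a table cell is off drug at relative level r, the arithmetic mean falls by p(1 − r). That is 0.41p at 2 days and 0.875p at 5 days. The documents do not give p.

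**Chance that an early EOT2 sample lands in a window.** Assume early EOT2 visits are spread evenly over the 96 × 7 = 672 days of TP1. The Week 24 and Week 48 windows cover 29 + 29 = 58 days, and 58/672 = 8.6%. The Week 96 window is left out because visits there are essentially those of completers, who are sampled one day after the last dose (Protocol 3.12.2.8), which is a true 24 h trough.

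**Planned-pregnancy interruptions.** These came with Amendment 7 (29 March 2017). Last planned entry was Q2 2011. Adding at most 96 weeks of TP1 and a gap of at most 3 months puts the latest P1 around mid to late 2013. Adding 156 weeks puts the latest P14 around mid to late 2016, before the amendment. On planned dates only P22 (Week 252) can be reached.

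**The case against.** The best counter-argument is that the SAP already limits the summary to pre-dose, trough-level samples, and that SAP 5.1.8 keeps assessments in pregnancy interruptions out of visit windows unless they are treatment-emergent. Neither acts as a filter here. A sample drawn before re-initiation is also pre-dose, and the SAP does not say how an EOT2 sample with no following dose is to be removed. The sentence in 5.1.8 belongs to the Table 3 windows and does not clearly reach the separate PK rules. If it did, it would still leave out other interruptions and post-discontinuation samples. SAP 5.1.3 does not name PK among the variables affected by pregnancy interruptions.

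Several limits do stand. The protocol states a study day only for Week 4. The other centres follow from the same convention, supported by Table 3 for Weeks 12, 24, 48, 72 and 96; Weeks 156 and 252 have no Table 3 row. Five days is the outer limit for an early EOT2 visit, so 12.5% is the worst case for that route. The output is descriptive, all objectives are exploratory, and Protocol 5.7 asks for the minimum and median, so a near-zero value would be visible.

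A reader might go further in four ways that the documents do not support:

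- That 20% of Week 4 samples are lost. The figure is a share of allowed days, and visits need not be evenly spread.
- That the SAP directs washed-out samples to be averaged. It only fails to keep them out.
- That pregnancy interruptions affect the trough tables generally. On planned dates they reach P22 only.
- That all three later TP1 windows count, giving 3 × 29 = 87 of 672 days (13%). The Week 96 window runs 14 days past Day 672 and holds essentially completers.

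**Conclusion.** Both defects are real. The day-count error is certain for Week 4, where the SAP contradicts an explicit protocol day. For the other seven windows it follows from the SAP's own Diff definition, its Day 8 and Day 15 windows and, where there is a row, Table 3. Its effect is small. Only samples on the last allowed day are dropped, and a sample one day early should still be at steady state, which Protocol 1.3.2.1 says is reached within 4–5 days.

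The missing on-drug condition has the larger potential effect per sample: a level of about 59% of the true trough at 2 days after the last dose, 12.5% at 5 days, and effectively nothing after a long interruption. These figures assume mono-exponential decay with the 32 h half-life. About 9% of early EOT2 visits would fall in the Week 24 or Week 48 window if evenly spread. That is a share of those visits, not of the samples in a table cell. The number of affected samples cannot be found in the documents, so the conclusion is that off-drug samples can enter the trough summaries, not that the means are materially biased. Overall the impact is minor to moderate, and the correction is worth making before the table is produced.

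**What to change.** In SAP 5.5.1, recentre the eight week-based windows on 7 × week + 1:

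- TP1: Week 4, 27–31; Week 24, 155–183; Week 48, 323–351; Week 96, 659–687.
- TP2/TP3: Week 12, 71–99; Week 72, 491–519; Week 156, 1079–1107; Week 252, 1751–1779.

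Leave Day 8 and Day 15 as they are.

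Add one condition: a sample enters the trough summaries only if the study drug log shows a dose on the day before sampling. List all other samples with the days since last dose. State that this rule also covers planned-pregnancy interruptions, so that it does not depend on how SAP 5.1.8 is read. Completers' EOT2 samples are kept, because they are taken one day after the last dose.

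The cost is a wording change and a small programming change. The drug log already identifies days without intake (SAP 5.4.1.1). The downside is that a few off-drug samples move from the table to a listing.
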